11.7 PK/PD

In order to explore the effects of cytisine on QTc prolongation, individual cytisine concentrations in plasma and individual (mean of triplicate recordings) absolute and change from baseline Holter QTcF values will be presented together in a listing. A scatter plot will be produced with the individual change from baseline Holter QTcF values at the extraction time points 0.5h, 1h, 2h, 3h, 4h, 6h, 8h, 12h and 24h plotted against the corresponding cytisine concentrations. Both dose groups will be presented on the same plot along with their correlation coefficients with plots for each age group (18-65, >65, all ages) presented separately.

Holter ECG versus plasma concentration data will be listed for the Safety Set and plotted for subjects in the ECG-PK Set.

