#### **4.2. Secondary Objectives**

[figure not shown]
1. To compare the PK parameters and tolerability for repeat dosing of 1.5 mg and 3.0 mg cytisine during the 25-day schedule in healthy smokers at 18-65 and >65 (elderly) years of age.
2. To assess the renal elimination of cytisine via measurement of urinary concentrations of cytisine during treatment on Day 1 and Day 25.
3. To evaluate for effects on QT/QTc interval prolongation and cardiac safety during treatment on Day 1 and Day 25 in healthy smokers at 18-65 and >65 (elderly) years of age.

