### **15.9.1. Holter ECGs**

The following ECG parameters will be extracted in triplicate from Holter recordings on Day 1 and Day 25 at 30 and 15 minutes prior to the first dose and 0.5 h, 1 h, 2 h, 3 h, 4 h, 6 h, 8 h, 12 h and 24 h post dose:

- Heart Rate (HR)
- PR intervals
- QRS
- QT
- QTcF

If a large change in heart rate is observed during the study, the individual QT correction method (QTcI) will be used as the primary QT correction method.

The extracted ECG parameters will be listed with any out of normal range values flagged (“H” -high or “L” -low). The ECG results will be assessed as either “normal” or “abnormal”. Any comments on abnormal results will also be provided. Descriptive statistics of absolute and change from baseline values at each time point will be tabulated by dose group and age group (18-65, >65 and overall).

In addition, frequencies of QTcF data will be calculated according to the following categories:

For absolute values:

- $QTcF \leq 450$  mSec
- $450 < QTcF \leq 480$  mSec
- $480 < QTcF \leq 500$  mSec
- $QTcF > 500$  mSec.

For change from baseline:

- QTcF increase  $\leq 30$  mSec
- $30 < QTcF$  increase  $\leq 60$  mSec
- QTcF increase  $> 60$  mSec.

Abnormalities in ECGs will be classified in terms of clinical significance. Clinically significant abnormalities will be reported as AEs. The number and percentage of subjects developing new ECG abnormalities will be summarised. The presence of outliers will be explored for heart rate, PR, QRS, QT and QTcF. Details of this analysis will be described in the Statistical Analysis Plan (SAP).

In order to explore the effects of cytisine on QTc prolongation, plasma concentrations will be plotted against change from baseline QTcF values.

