2 STUDY OBJECTIVES

Primary Objectives:

The primary objectives of this study are:

- to evaluate the pharmacokinetic (PK) parameters during repeat dosing of 1.5 mg or 3.0 mg cytisine when administered as the commercial 25-day schedule;
- to evaluate the pharmacodynamic (PD) effects (e.g. reduction in smoking) with repeat dosing of 1.5 mg or 3.0 mg cytisine when administered as the commercial 25-day schedule.

Secondary Objectives:

The secondary objectives of this study are:

[figure not shown]
- to compare the PK parameters and tolerability for repeat dosing of 1.5 mg and 3.0 mg cytisine during the 25-day schedule in healthy smokers at 18-65 and >65 (elderly) years of age;
- to assess the renal elimination of cytisine via measurement of urinary concentrations of cytisine during treatment on Day 1 and Day 25;
- to evaluate for effects on QT/QTc interval prolongation and cardiac safety during treatment on Day 1 and Day 25 in healthy smokers at 18-65 and >65 (elderly) years of age.

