3.5 SAMPLE SIZE CONSIDERATIONS

A total of approximately 36 subjects will be randomised to the study, with approximately 18 subjects per treatment arm (12 aged 18-65 and 6 aged >65).

No previous pharmacokinetic studies with cytisine have reported the effects of repeated administration, so no estimates of intra-subject variability of C_{max} , C_{min} or AUC are available. No specific hypothesis testing is planned. Post-hoc analyses may be performed for PK or PD effects that may appear significantly different between the dosage groups or age groups. In general, the sample size of 36 should be sufficient to meet the exploratory objectives of the study.

Subjects who withdraw from study at any time after randomisation will not be automatically replaced. Replacement based on the number and reason of withdrawals will be at discretion of the Sponsor, following discussion with the Principal Investigator.

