11.4.1 Plasma Concentration Data

Plasma PK samples will be collected for measurement of cytosine at the following time points:

- Day 1, first dose: Pre-first dose, 0.5h, 0.75h, 1h, 1.25h, 1.5h, 2h;
- Day 1, last dose: Pre-last dose, 0.5h, 1h, 1.5h, 2h, 2.5h, 3h, 3.5h, 4h, 5h;
- Days 2 and 3: Pre-last dose, 0.5h, 1h, 1.5h, 2h, 2.5h, 3h, 3.5h, 4h, 5h;
- Days 4, 13, 17, 21: Pre-first dose;
- Days 12, 16, 20, 24: Pre-last dose, 1h, 1.5h, 2h, 2.5h, 3h, 3.5h, 4h;
- Day 25: Pre-dose, 0.5h, 0.75h, 1h, 1.25h, 1.5h, 1.75h, 2h, 2.25h, 2.5h, 2.75h, 3h, 3.25h, 3.5h, 3.75h, 4h, 5h, 6h, 8h, 10h, 12h, 24h.

Cytosine concentrations in plasma will be listed and summarised by dose group and age group using the descriptive statistics N, n, arithmetic mean, arithmetic standard deviation (SD), coefficient of variation (CV%), minimum, median and maximum.

The individual subject plasma cytosine concentration profiles over time will be presented graphically using actual blood sampling times on a linear and semi-logarithmic scale. Arithmetic mean plasma cytosine concentration profiles over time will be presented on linear and semi-logarithmic scales with profiles presented for each study day as appropriate and a separate plot for each dose group and age group.

For inclusion within the summary tables and linear scale plots, concentrations below the limit of quantification (BLQ) will be assigned a value of zero. For inclusion within the semi-logarithmic scale plots, concentrations below the limit of quantification (BLQ) will be set to missing. Concentrations above the upper limit of quantification (ULOQ) will be obtained via dilution into the calibration range and are valid results.

Plasma concentration data listings and individual plots will be presented using the Safety Set. Plasma concentration data summaries and mean plots will be presented using the PK Set and the Safety Set. All plasma concentration data included in listings and summaries will be presented to three significant figures.

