11.6.4.2 Holter Monitoring

The ECG extraction time points will be from extraction windows which precede the PK blood draws. ECG parameters (heart rate, PR interval, QRS duration, QT interval and QTcF interval) will be extracted in triplicate from Holter recordings on Day 1 and Day 25 at 30 and 15 minutes prior to the first dose and at 0.5h, 1h, 2h, 3h, 4h, 6h, 8h, 12h and 24h post dose.

The extracted ECG parameters will be listed with any out of normal range values (see Appendix 1) flagged (flag 'H' or 'L' appended to relevant result). The ECG results will also be assessed as either 'normal' or 'abnormal' with comments on abnormal results also presented.

The mean of the triplicate recordings at each time point will be calculated for use in the summary tables and plots. Any ECG traces that are determined to contain a technical error will not be included in the calculation of the mean values. At each time point, the mean value will be derived from all ECGs (generally three) that are free of technical errors. Descriptive statistics (N, n, mean, SD, minimum, median and maximum) of absolute and change from baseline (see definition, Section 5) values on Day 1 and Day 25 at each time point up to 24h, will be tabulated for each dose group and age group. The change from baseline ECG results will also be plotted over time by dose group and age group.

In addition, frequencies of QTcF data will be calculated according to the following categories:

For absolute values:

- QTcF > 450 mSec
- QTcF > 480 mSec
- QTcF > 500 mSec

For change from baseline:

- QTcF increase > 30 mSec
- QTcF increase > 60 mSec.

The presence of outliers will be explored for heart rate, PR interval, QRS duration, QT interval and QTcF interval). The outlier analysis will use the time-averaged baseline (see definition, Section 5) and compare that baseline value to each of the individual on-treatment ECG time point values. Outliers are defined as follows for this analysis:

- Heart rate: A value for a subject will be considered to be an outlier at a pre-defined post dose time point if the heart rate measurement at that time point is <50 bpm and the measure is at least a 25% decrease from the subject's baseline mean heart rate (i.e., a bradycardic event) or if the heart rate measurement at the pre-defined post dose time point is >100 bpm and the measure is at least a 25% increase from the baseline mean heart rate (i.e., a tachycardic event).

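### The concentration-QTcF relation is summarised only by a correlation over clustered repeated pairs, which gives no QTcF change in ms per unit concentration and no interval

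*SAP*

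**What the plan says.** QTc is a secondary objective: "To evaluate for effects on QT/QTc interval prolongation and cardiac safety during treatment on Day 1 and Day 25" (Protocol 4.2, repeated in SAP Section 2). Protocol Section 3 adds that any QT effect will be analysed in relation to the pharmacokinetic profile.

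Protocol 15.9.1 provides only a graph: "plasma concentrations will be plotted against change from baseline QTcF values". SAP 11.7 goes a little further. "A scatter plot will be produced with the individual change from baseline Holter QTcF values at the extraction time points" (0.5, 1, 2, 3, 4, 6, 8, 12 and 24 h), against the corresponding concentrations, and "Both dose groups will be presented on the same plot along with their correlation coefficients with plots for each age group". The text names no type of coefficient, subject term, slope, prediction or interval.

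SAP 11.6.4.2 has the ECGs "extracted in triplicate from Holter recordings on Day 1 and Day 25 at 30 and 15 minutes prior to the first dose" and at the nine later times. It tabulates change from baseline in ms by time point, dose group and age group, and adds threshold counts and outliers. It plans no confidence intervals there and does not use concentration. SAP Section 5 defines one Holter baseline per subject, the Day 1 pre-dose mean, for both days.

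**The concern.** The points on the plot are not separate observations. A subject's pairs share one baseline and one person's QTcF level, and they fall on two recording days. A plain correlation over them blends two questions: whether subjects with higher exposure have larger changes, and whether a given subject's QTcF moves with concentration. It also depends on how noisy QTcF is and how widely concentrations are spread, so it cannot be turned back into ms.

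The study has no placebo arm, so the relation to exposure is the natural way to read the QTcF data. A weak coefficient could accompany a relevant slope, and a sizeable one could reflect clustering. The SAP handles repeats properly elsewhere: the Cmax and Cmin schedule comparison in 11.4.3.1 has a random subject effect.

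**Working it through.** The documents give no QTc precision or power figure, so there is none to reproduce. They also give no QTcF variance. Every QTcF SD below is an assumption, shown as a range.

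**1. Pairs per subject.** ECG times are from SAP 11.6.4.2 and draws from SAP 11.4.1.
- Day 1, by schedule: "Day 1, first dose: Pre-first dose, 0.5h, 0.75h, 1h, 1.25h, 1.5h, 2h" matches the ECGs at 0.5, 1 and 2 h only.
- Day 1, 12 h: this matches the draw 2 h after the last dose only if the sixth dose falls at about 10 h (5 intervals of 2 h). The intervals are described as approximate, so this is an assumption.
- Day 1, 3, 4, 6, 8 and 24 h: no draw exists, although 11.7 lists these times.
- Day 25: all nine times match.

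Total 4 + 9 = 13. The groups are "with approximately 18 subjects per treatment arm (12 aged 18-65 and 6 aged >65", so there are 18 × 13 = 234 pairs per dose group, 36 × 13 = 468 overall, and 6 × 13 = 78 per dose group in the >65 plot.

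**2. Clustering.** The design effect for a mean is 1 + (13 − 1) × ICC. At ICC 0.2, 0.5 and 0.7 it is 3.4, 7.0 and 9.4, so 234 points carry about as much information as 234/3.4 = 69, 234/7.0 = 33 and 234/9.4 = 25 independent ones.

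**3. Spread of concentrations at 3.0 mg.** Take a one-compartment curve with the Protocol Table 1 means: AUCinf 73.63 ng·h/mL after 1.5 mg, λz 0.1758 per h, ka 2.81 per h. Then CL/F = 1500/73.63 = 20.4 L/h and V/F = 20.37/0.1758 = 115.9 L. Superpose C(t) = (D/V) × ka/(ka − λz) × (e^(−λz·t) − e^(−ka·t)).
- Day 1: 18.5, 21.5 and 19.3 ng/mL at 0.5, 1 and 2 h, then 57.5 at 12 h.
- Day 25, with carry-over from two Day 24 doses 6 h apart: peak 22.8 at 1 h, falling to 0.4 at 24 h.

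The curve peaks below the observed single-dose mean of 27.76 ng/mL (Protocol 2.3.2), so the ratio is more reliable than the level. The Day 1 12 h pair is 57.5/22.8 = 2.5 times the highest other pair. Across the 13 values the mean is 17.9 and the variance 178, so this pair supplies (57.5 − 17.9)²/(13 × 178) = 68% of the spread within a typical subject. With an assumed between-subject CV of 40%, the SD over all points is √(1.16 × (178 + 17.9²) − 17.9²) = 16 ng/mL. Without the 12 h pair (mean 14.6, variance 51.7) it is 9.7.

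**4. The coefficient does not fix the effect.** For slope β, concentration SD s, and between- and within-subject SDs b and w, r ≈ βs/√(β²s² + b² + w²). With β = 0.2 ms per ng/mL (0.2 × 40 = 8 ms at 40 ng/mL) and s = 16:
- b/w = 3/4: 3.2/√(10.24 + 25) = 0.54
- b/w = 6/6: 3.2/√(10.24 + 72) = 0.35
- b/w = 9/10: 3.2/√(10.24 + 181) = 0.23

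Simulation of 18 subjects × 13 pairs gave means of 0.49, 0.33 and 0.22. At 6/6, dropping the 12 h pair alone lowers r from 0.35 to 1.94/√(3.76 + 72) = 0.22 with the same slope.

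**5. What a mixed model would give.** These are generalised least squares standard errors for 36 subjects. The variance components are treated as known: random intercept SD b, residual SD w, slope SD 0.1 ms per ng/mL, subject-by-day SD 3 ms. The reference concentration is 27.76 ng/mL, and the 90% half-width is 1.645 × SE. The baseline covariate is left out.

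| Assumed b/w (ms) | 4/5 | 6/6 | 8/8 | 10/10 |
|---|---|---|---|---|
| Half-width, no day term (ms) | 1.6 | 2.1 | 2.6 | 3.2 |
| Half-width, day term (ms) | 1.86 | 2.32 | 2.88 | 3.47 |
| Half-width, day term, no 12 h pair (ms) | 2.17 | 2.67 | 3.35 | 4.03 |
| Slope SE, day term | 0.032 | 0.037 | 0.045 | 0.053 |
| Slope SE, day and time-point terms | 0.036 | 0.041 | 0.051 | 0.060 |
| Slope SE, day term, no 12 h pair | 0.049 | 0.057 | 0.072 | 0.087 |
| Slope SE, day and time-point terms, no 12 h pair | 0.093 | 0.110 | 0.136 | 0.168 |

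Slope SEs are in ms per ng/mL. The last row is about three times the fourth, so much of the apparent precision rests on one evening pair per subject. For the 12 subjects over 65 alone, the half-width without a day term is 2.8 to 5.6 ms.

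**The case against.** The best defence is that nothing planned is invalid. The protocol promised only a plot, 11.7 is labelled as exploration, and SAP 3.5 plans no hypothesis test. A reader might infer an inflated false-positive rate. Simulation with 6/6 ms SDs and no true mean slope does give nominal 5% rejections of about 8–9% with random intercepts only, 11–12% with a day effect added, and 14–43% with random slopes. But no p-value, interval or decision rule is attached to the coefficient, so these figures describe a use that the SAP does not plan. That part of the defence stands.

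A reader might also infer that the SAP reports no QTc effect in ms. It does, in 11.6.4.2, including at 0.5, 1 and 2 h, near the expected peak. A mean prolongation at those times would be visible whatever the coefficient showed. What those tables lack is an interval and a link to concentration.

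Nor are the two doses merged into one coefficient. The wording reads as one per dose group, pooled over subjects, times and days. The figure shells are blacked out, so the type of coefficient or a fitted line may be specified there.

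Finally, the replacement has limits. Concentration follows the clock, Day 1 starts fasted while Day 25 follows breakfast (Protocol 7.2.2), and smoking should change in between. These limits are real, but the correlation has the same confounding with no adjustment and no interval.

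**Conclusion.** The point holds as one of interpretation. Section 11.7 meets the aim of relating QTcF to exposure with a unitless number that depends on QTcF noise, on clustering and on which pairs happen to enter. The same 8 ms effect at 40 ng/mL can appear as a correlation of about 0.5 or 0.2. A mixed model on the same pairs would give a change in ms with a 90% half-width of about 1.9 to 3.5 ms, or 2.2 to 4.0 ms without the Day 1 12 h pair.

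These sizes rest on assumed QTcF variances, one-compartment profiles and, where the 12 h pair is used, a sixth dose at about 10 h. The documents do not support a claim that a planned test is invalid or that QTcF change in ms goes unreported. Nor would the model, without placebo, isolate a drug effect or by itself exclude QTc prolongation. This is a worthwhile, inexpensive improvement to an exploratory analysis.

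**What to change.** Keep the scatter plot and listing, and amend SAP 11.7 as follows.

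- **Model, in place of the coefficient:** a linear mixed model of change in QTcF on concentration, with centred baseline QTcF, a study-day effect and a subject random intercept (random slope if estimable), both dose groups together, labelled exploratory.
- **Pairs:** all nine times on Day 25; 0.5, 1 and 2 h on Day 1; 12 h on Day 1 only where a draw actually coincides. State that Day 1 has no matching draw at 3, 4, 6, 8 or 24 h.
- **Report:** the slope, and the predicted QTcF change with 90% CI at the geometric mean Day 25 Cmax of each dose group. The day must be named because Cmax is derived on nine occasions and Holter covers only Days 1 and 25. Flag any prediction beyond the observed Holter-day concentrations as extrapolation.
- **Sensitivity fits:** without the Day 1 12 h pair, and with a time-of-day term.
- **Stated limits:** no placebo arm; Day 1 fasted and Day 25 fed; time, meal and smoking change not separable from drug effect.

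The cost is a paragraph of SAP text and one model with its sensitivity fits, on data already collected. The price in precision is a wider interval when a time term is added, and random slopes may fail to converge with 36 subjects, so the SAP should name the intercept-only model as the fallback.

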11.8 OTHER

11.8.1 Prior and Concomitant Medications

All medications will be coded using the WHO Drug Dictionary (version as specified in the DMP) and listed using the ATC Level 4 class, Preferred Term and verbatim text. A medication will be regarded as 'prior' if it stops prior to dosing, 'prior and ongoing' if it starts prior to dosing and continues after dosing and 'concomitant' if it starts after dosing. Frequencies of prior medications and concomitant medications within an ATC Level 4 class and Preferred Term will be presented by dose group, age group and overall. Medications regarded as 'prior and ongoing' will be assigned to treatment and included within the summary of concomitant medications.

11.8.2 Extent of Exposure

Exposure will be summarized by dose group and age group using counts and percentages for categorical variables and descriptive statistics (N, n, mean, SD, minimum, median and maximum) for continuous variables. The following will be calculated for each subject and summarized by dose group, age group and overall: duration of exposure to cytisine (days), number of cytisine doses administered, total dose of cytisine (mg) administered, percentage of planned dose of cytisine administered. One-hundred (100) doses of cytisine are to be administered over 25 days. The total planned dose of cytisine is 100 x 1.5 mg in the 1.5 mg dose group and 100 x 3.0 mg in the 3.0 mg dose group. Duration of exposure to cytisine will be summarized both as a categorical variable and as a continuous variable.

11.8.3 All Other Data

All data will be listed, including the following: Tobacco and Alcohol Use, Visit Dates, Medical History and Concurrent Conditions, Menstrual and Obstetric History, Pregnancy Test Results, Eligibility Check, Physical Examination, Inclusion/Exclusion Criteria Failures, Virology Results, Alcohol and Drugs of Abuse Results, Dose Administration, Urine Volumes, Additional Notes, Holter Monitoring Information and Daily Smoking and Study Medication Diary, Drug Accountability, Fagerström Test for Nicotine Dependence Questionnaire.

Derivations within listings:

PK Blood Sampling Time Deviations: Calculate sample time deviation as: actual time – theoretical time, display in minutes.

Analysis Sets: Detail whether subject should be included in each of the analysis sets along with corresponding comments if not included.

Inclusion/Exclusion Criteria: Only failures to be recorded. If no failures display *'All subjects passed inclusion/exclusion criteria'*.

Protocol Deviations: Major/minor classification to be assigned and confirmed by Sponsor.

Fagerström Test for Nicotine Dependence Questionnaire: The FTND responses will be assigned numerical values as follows:

- A question with a yes/no response: 'No' = 0; 'Yes' = 1.
- How soon after you wake up do you smoke your first cigarette: 'After 60 minutes' = 0; '31 – 60 minutes' = 1; '6 – 30 minutes' = 2; 'Within 5 minutes' = 3.
- Which cigarette would you hate most to give up: 'All others' = 0; 'The first one in the morning' = 1.
- How many cigarettes in a day do you smoke: '10 or less' = 0; '11 – 20' = 1; '21 – 30' = 2; '31 or more' = 3.

The FTND total score is defined as the sum of the scores from all 6 questions, provided all 6 questions have been completed. If any of the questions have a missing response, the total score will not be calculated.

12 VALIDATION

All tables, figures and listings will be subject to independent quality control and visual review. Unique tables will be independently programmed. Findings will be documented in an Output Summary file quality control form and actions taken will also be documented.

The study summary sheet of the Output Summary file will be completed and signed by all persons who performed QC. The final version of the Output Summary, including the signed summary sheet, will be printed and stored in the Data Management File. The study summary sheet of the Output Summary file will be completed and signed by all persons who performed QC. The final version of the Output Summary, including the signed summary sheet, will be printed and stored in the Data Management File (DMF).

13 LITERATURE CITATIONS/REFERENCES

None.

14 LIST OF TABLES, FIGURES AND LISTINGS

List of Tables and Figures Contained in Report Section 14

14.1 Disposition and Demographic Data

14.1.1 Disposition Data

Table 14.1.1.1	Summary of Study Disposition	Safety Set
----------------	------------------------------	------------

14.1.2 Demographic Data

Table 14.1.2.1	Summary of Demographic Data	Safety Set
Table 14.1.2.2	Summary of Demographic Data - (if applicable)	PK Set

